Contact lens wearers often report dry eye symptoms and show signs of MGD including gland atrophy, thinned lipid layer, and increased tear film instability.⁶⁻⁸ It has been shown that in many patients with intolerance to contact lenses, MGD has been observed. Therefore, treatment of MGD may support functioning of the meibomian glands and lead to improvement in patient contact lens comfort. Warm compresses are a commonly prescribed treatment method for applying localized heat to the meibomian glands to improve secretion.⁹⁻¹¹ With good patient compliance, warm compresses have been shown to be an adequate supplemental therapy for MGD as the heat softens meibum in glands that are obstructed allowing for secretion into the tear film. Many methods of applying heat to the eyelids for treatment of MGD exist; however, the results of the different methods can vary based on the heating method, how long the compress is applied, and whether the compress remains hot for the duration of application. Because of the sometimes seemingly ineffectiveness of the therapy due to variation in methods and no accepted standard, patient compliance for home therapy often wanes and further reduces the likelihood of successful treatment. Therefore, the purpose of this study is to assess the potential benefits of using the Bruder Moist Heat Compress, a warm compress capable of maintain heat effectively, in contact lens wearers with MGD.

Study Design & Endpoints

This will be a prospective, three-arm, randomized controlled study to evaluate the benefits of using the Bruder Moist Heat Compress in contact lens wearers who report reduced comfortable wearing time by assessing improvement in MG function and comfortable contact lens wearing time after one month of daily warm compress application. All subjects will undergo examination to determine eligibility and capture baseline status. Study endpoints will be evaluated after one month.

Thirty adults who currently wear contact lenses, who report reduced contact lens wear time will be enrolled in the study. Subjects will be randomized to either one of two treatment arms or a control arm with approximately ten subjects per group; that is, subjects will be randomized to one of the following study arms:

- 1) Application of Bruder Moist Heat Compress twice daily for one month (ten minute application in the morning prior to contact lens insertion and ten minute application in the evening after lens removal)
- 2) Application of Bruder Moist Heat Compress once daily for one month (ten minute application in the evening after lens removal)
- 3) Application of warm wash cloth twice daily (ten minute application each time) for one month (control group)

Subjects will be seen for three study visits over a period of four weeks according to the following visit schedule:

- Visit 1 (Screening & Randomization, Day 1)
- Visit 2 (Day 15 \pm 2 days)
- Visit 3 (Final Visit, Day 29 \pm 1 day)

The procedures to be performed during the visits include:

1. Questionnaires: CLDEQ long form, SPEED, OSDI
2. Medical and Ophthalmic History
3. Habitual visual acuity with contact lenses
4. Contact Lens fit assessment
5. LipiView to measure tear film thickness
6. Slit lamp examination
7. Tear film break up time
8. Corneal Staining
9. MG assessment
10. Meibography
11. Corneal Topography

Each visit will take approximately 45 minutes. Subjects will be instructed to apply the Bruder Moist Heat Compress after removal or prior to insertion of contact lenses. Subjects will heat the compress according to the instructions on the package, namely: heat for twenty-five seconds in the microwave, and depending on the microwave wattage increase by increments of five seconds to not exceed a total of thirty-five seconds. Once heated, subjects will apply the compress to closed eyelids for ten minutes. During the treatment period, subjects will complete a daily diary that captures insertion and removal time of contact lenses, as well as the time comfortable contact lens wear ends. Diaries will also be used to ensure subject compliance of application of the Bruder compress.

Study Objectives

Primary Objective: To show that daily application of the Bruder Moist Heat Compress in subjects with MGD who experience CL discomfort can result in an increase in comfortable contact lens wear time

Secondary Objective: To compare the efficacy of once daily application of the Bruder Moist Heat Compress versus twice daily application

Tertiary Objective: To show that the Bruder Moist Heat Compress is an effective treatment for improving meibomian gland function in symptomatic contact lens wearers

Study Endpoints

Primary: Mean change from baseline in the duration of subject-reported comfortable contact lens daily wear time (hours per day) at the week four visit

Secondary: Mean change in comfortable contact lens wear time (hours per day) in twice daily application group compared to once daily application group

Tertiary: Mean change in total meibomian gland score in treatment groups using the Bruder Moist Heat Compress compared to controls from baseline to four weeks

Inclusion Criteria:

1. 18 years or older
2. Provide informed consent and authorization to disclose protected health information
3. Have habitual contact lens corrected visual acuity in each eye of at least 20/30
4. Willing to comply with protocol
5. Wear soft daily contact lenses for total wear time of at least 4 hours a day and at least 4 days a week on average over at least a 30 day period before enrollment
6. Have a diagnosis of Contact Lens Dry Eye based on the CLDEQ results
7. Have at least a 2 hour difference between overall wear time and comfortable wear time of contact lenses
8. Assess that the contact lens fit/material/disinfection solution are acceptable and not reasons for CL discomfort

Exclusion Criteria:

1. Have any uncontrolled systemic disease that in the investigator's opinion could be expected to interfere with the study, for example, conditions associated with dry eye disease
2. Pregnant by self-report
3. Active ocular conditions: infection, allergic conjunctivitis, severe eyelid inflammation including anterior blepharitis
4. Have a clinically significant ophthalmic abnormality noted during examination or per subject history
5. Have changed the brand of contact lenses or care solutions within 30 days prior to screening or anticipates the need to change current type or brand of contact lenses or care solutions
6. Any overnight wear of contact lenses or daily disposable contact lenses
7. Require use of prescribed topical ophthalmic medications
8. Participation in a clinical trial in the past 30 days
9. Any previous refractive or corneal surgery (e.g., PRK, LASIK, radial keratotomy, etc.)
10. In the opinion of the investigator, be unwilling or unable to comply with the study protocol
11. Have temporary and/or permanent punctal plugs in either or both eyes
12. Have initiated or altered the dosage of omega-3 dietary supplements in the past 30 days

References

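### Comfortable wear time has no diary baseline, and the baseline report also feeds the 2-hour entry criterion, so the primary change from baseline, which names no comparator, can show a spurious increase within arms

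*Protocol*

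**What the plan says.** All of this is in the Protocol.

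- **Diary (Study Design & Endpoints).** "During the treatment period, subjects will complete a daily diary that captures insertion and removal time of contact lenses, as well as the time comfortable". The sentence is cut here; its last item is the moment at which comfort stops each day. No other listed procedure is said to record when comfort ends. The visit questionnaires are CLDEQ, SPEED and OSDI.
- **Visit schedule.** The first contact is "Visit 1 (Screening & Randomization, Day 1"). The same section has one examination both settle eligibility and supply baseline status. There is no run-in.
- **Inclusion 7.** "Have at least a 2 hour difference between overall wear time and comfortable wear time of contact lenses".
- **Primary endpoint.** "Mean change from baseline in the duration of subject-reported comfortable contact lens daily wear time (hours per day) at the week four visit". The secondary and tertiary endpoints each name a comparison group; this one does not.
- **Primary objective.** To show that daily use of the compress "can result in an increase in comfortable contact lens wear time". The control arm is not mentioned.

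The protocol does not say how comfortable wear time is obtained at Visit 1, or whether the week-four value comes from the diary or from a report at the visit.

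**The concern.** The baseline value of the primary variable is one of the two components of the gap that admits the subject. When the gap is reported with error, a cut at 2 h preferentially admits subjects whose comfortable time was under-reported on that occasion. A later measurement drifts back up, and the change from baseline is positive without any treatment effect. No second pre-treatment measurement exists to absorb this.

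A second mechanism applies only if week four is read from the diary. The change then subtracts a reported typical day from clock times recorded daily, and any systematic difference between the two methods enters the endpoint.

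At stake is the primary claim as worded: an increase from baseline, with no comparator. A statistical analysis plan can choose the estimator and the contrast, but it cannot supply a pre-treatment diary that was never collected.

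**Working it through.** The protocol gives no SD, effect size, alpha or power for comfortable wear time, so there is no figure to reproduce. The check asks how large a change appears when treatment does nothing. From the protocol come the 2 h cut, 30 subjects in three arms of about 10, and hence about 20 in the two compress arms. **Every distributional input below is an assumption.**

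**1. Closed form.** Let the reported gap be normal with mean μ and SD σ, with all its error in comfortable time and test-retest correlation r.

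Mean excess among those selected = σ·φ(a)/[1 − Φ(a)], with a = (2 − μ)/σ.

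Spurious gain = (1 − r) × excess.

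For μ = 2, σ = 1.5: a = 0, excess = 1.5 × 0.3989/0.5 = 1.20 h, so the mean reported gap at entry is 3.20 h. At r = 0.5 the gain is 0.5 × 1.20 = 0.60 h.

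| μ (h) | σ (h) | Excess (h) | Gain, r = 0.5 | r = 0.7 | r = 0.9 |
|---|---|---|---|---|---|
| 2 | 1.5 | 1.20 | 0.60 | 0.36 | 0.12 |
| 2 | 2.0 | 1.60 | 0.80 | 0.48 | 0.16 |
| 3 | 1.5 | 0.64 | 0.32 | 0.19 | 0.06 |
| 4 | 1.5 | 0.27 | 0.14 | 0.08 | 0.03 |

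**2. Effect on a within-arm test.** This is a one-sample t test, n = 20, two-sided 5%, by noncentral t with noncentrality gain × √20 / SD of change. With a gain of 0.6 h it rejects in 40% of trials at SD 1.5 h and 25% at SD 2 h. With SD 1.5 h, rejection is 15%, 9% and 5% at μ = 3 (r = 0.5, 0.7, 0.9), and 5 to 7% at μ = 4.

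**3. Simulation under a different model.** Overall wear is N(12, 2) h. The true gap has SD 1.5 h and is floored at 0. Visit 1 error has SD 0.5 h in overall time and 0.5, 1.0 or 1.5 h in comfortable time. Week-four error has SD 0.5 h. Subjects enter if the reported gap is at least 2 h, and there is no treatment effect.

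| Mean true gap (h) | Error SD (h) | Null change (h/day) | Within-arm rejection, n = 10 | n = 20 | Between-arm rejection, 10 v 10 |
|---|---|---|---|---|---|
| 2 | 0.5 | +0.12 | 7.6% | 11.2% | 5.0% |
| 2 | 1.0 | +0.43 | 22.0% | 42.7% | 5.0% |
| 2 | 1.5 | +0.84 | 41.2% | 74.9% | 4.7% |
| 3 | 0.5 | +0.07 | 6.2% | 7.5% | 5.2% |
| 3 | 1.0 | +0.26 | 11.0% | 18.3% | 5.0% |
| 3 | 1.5 | +0.55 | 18.8% | 38.4% | 4.7% |
| 4 | 0.5 | +0.03 | 5.2% | 5.4% | 4.7% |
| 4 | 1.0 | +0.14 | 6.5% | 8.5% | 5.3% |
| 4 | 1.5 | +0.33 | 9.4% | 16.1% | 5.0% |

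The between-arm mean difference stays within 0.01 h of zero in every row.

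**4. Instrument shift.** In the row with mean gap 3 h and error SD 1.0 h, suppose Visit 1 reports also understate comfortable time by 0.5 h relative to the week-four measure. The null change then rises from +0.26 to +0.70 h.

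**The case against.** The strongest reply is that this is a randomized trial with a washcloth control. Selection, baseline method and week-four method are the same in all arms, so the drift cancels in any between-arm contrast. That stands, and the simulation confirms it. A reader might infer that the treatment comparison itself is biased; it is not. The cost there is precision, because a single report is likely to track later diary values less closely than a diary mean would. That loss is not quantified here.

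Four further points stand in part.

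- **No within-arm test is prescribed.** The protocol specifies no test, and an analysis plan may compare arms. The rejection rates within arms show what a literal reading of the endpoint risks, not what the trial is known to do. But neither the primary endpoint nor the primary objective names the control, so that reading is open.
- **The recall-to-diary switch is not established.** It is tempting to say that the protocol mixes instruments. The endpoint wording also fits a report at the visit. If the same question is asked both times, the shift goes and the selection effect remains.
- **Inclusion 7 is a gap, not a low value on one day.** A subject with 14 h overall and 12 h comfortable qualifies. The neighbouring wear criterion is an average over at least 30 days; if the gap is judged on the same basis, reports should be more stable and r higher. Error in reported overall time also weakens the drift.
- **A mean gap at the cut is unfavourable.** It makes half of candidates fail. The trial recruits people already reporting reduced wear time, so a higher mean is plausible, and the drift is then smaller.

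**Conclusion.** The point holds for within-arm change and should be fixed. No pre-treatment diary value will exist, and the Visit 1 report serves as both entry test and baseline, so the primary endpoint as worded is open to a spurious increase. Its direction is upward in every scenario examined. Its size is an assumption: about 0.03 to 0.8 h/day from selection alone, near zero if reports are reliable or most true gaps are well above 2 h, and larger if week four comes from the diary and Visit 1 reports understate comfortable time. That the baseline is recall is inferred from the one-day screening and the 30-day look-back for wear; the protocol does not name the method.

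The documents do not support a conclusion that the randomized comparison is biased, or that a high false-positive rate is built into the trial. The 25 to 40% figures need a 0.6 h drift, which in the closed form means a mean gap at the cut and r = 0.5. At mean gaps of 3 to 4 h the same closed form gives about 5 to 15%. The simulation gives 5 to 38% at those gaps, with the upper end requiring a recall error SD of 1.5 h.

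**What to change.** **Preferred.** Keep Inclusion 7 on the Visit 1 report, but separate it from baseline. Hand out the existing diary at Visit 1 and have it kept for about 7 days before randomization and first application. Define baseline as the mean over lens-wearing days of that run-in. Define week four as the mean over lens-wearing days among the last 7 diary days before Visit 3. The cost is about one week and one short extra contact for each of 30 subjects, with the visit schedule reworded to match. It must be decided before enrolment, because the data cannot be recovered later.

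**If no run-in is feasible.** Take baseline and week four from one identical question asked at Visits 1 and 3, with the diary as supportive. This costs wording only. It removes any instrument shift but not regression to the mean, which should be stated as a limit on any within-arm claim.

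**In either case.** Reword the primary endpoint and objective so that the claim rests on the baseline-adjusted difference in change between the compress arms and the washcloth control. Report within-arm change descriptively. This also costs wording only.

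### The diary compliance check names only the Bruder compress, so adherence monitoring can differ between the Bruder groups and the wash-cloth control in the tertiary comparison

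*Protocol*

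**What the plan says.** All the relevant text is in the protocol, mostly under Study Design & Endpoints.

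- **Arm 1** uses the compress twice daily, timed around lens wear: "ten minute application in the morning prior to contact lens insertion and ten minute application in the evening after lens removal".
- **Arm 2** is also timed: "Application of Bruder Moist Heat Compress once daily for one month (ten minute application in the evening after lens removal".
- **Arm 3** has a frequency, a duration and a course length, but no time of day and no relation to lens wear: "Application of warm wash cloth twice daily (ten minute application each time) for one month (control group".
- **Application instruction**: "Subjects will be instructed to apply the Bruder Moist Heat Compress after removal or prior to insertion of contact lenses".
- **Diary contents**: "subjects will complete a daily diary that captures insertion and removal time of contact lenses", plus the time at which comfortable wear ends. Applications of treatment are not among the listed items.
- **Compliance check**: "Diaries will also be used to ensure subject compliance of application of the Bruder compress".

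Under Study Endpoints, the tertiary endpoint is "Mean change in total meibomian gland score in treatment groups using the Bruder Moist Heat Compress compared to controls", from baseline to four weeks. The background remarks that "patient compliance for home therapy often wanes and further reduces the likelihood of successful treatment".

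**The concern.** The protocol itself treats adherence as a determinant of whether home heat therapy works. A comparison of one home heat therapy with another then needs use of the assigned treatment to be recorded and checked in the same way on both sides. The written check covers one side only.

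Interpretation of the tertiary result is at stake. If the gland score improves more in the Bruder groups, the reader will want to know whether the cloth was used as scheduled. If it does not, the same question arises. Without records of cloth use neither can be answered. This is a matter of trial conduct: an analysis plan can decide how to use adherence data but cannot create them after the month has passed.

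**Working it through.** The protocol gives no figure to reproduce here, so the main check sets the text out arm by arm.

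| Item | Arm 1 (compress, twice daily) | Arm 2 (compress, once daily) | Arm 3 (wash cloth, twice daily) |
|---|---|---|---|
| Frequency and ten-minute duration stated | yes | yes | yes |
| Timing around lens wear stated | yes | yes | no |
| Covered by the general timing instruction | yes | yes | not named |
| Keeps the daily diary (lens times) | yes | yes | yes |
| Covered by the diary compliance check | yes | yes | not named |
| Used in the tertiary comparison | yes | yes | yes |

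The wash cloth is mentioned nowhere outside the arm 3 line, so no other sentence fills the two gaps.

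**Which endpoints are touched.** The primary endpoint is a mean change from baseline and names no comparator. The secondary endpoint compares twice-daily with once-daily compress use and does not involve the cloth. Only the tertiary endpoint names controls.

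**Can a direction of bias be derived?** Scheduled applications per subject, taking Day 1 to Day 29 as 28 days of treatment:

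- arm 1: 2 × 28 = 56
- arm 2: 1 × 28 = 28
- arm 3: 2 × 28 = 56

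With about ten subjects per arm, the two Bruder groups together average (56 + 28) / 2 = 42 scheduled applications, which is 42 / 56 = 75% of the control's schedule.

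Suppose, as an illustration only, that compress and cloth are equally effective per application, that benefit is proportional to applications made, and that compress adherence is complete. Then:

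- control adherence 100%: 56 applications against 42, which favours the control
- control adherence 80%: 0.80 × 56 = 44.8 against 42, which still favours the control
- control adherence 75%: 0.75 × 56 = 42 against 42, no difference
- control adherence 50%: 0.50 × 56 = 28 against 42, which favours the device

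For arm 1 alone against control (56 against 56), any shortfall in cloth use favours the device under the same assumptions. The sign thus depends on control adherence, which the protocol does not give, and on whether the Bruder groups are taken singly or together. The size depends further on the effect per application and on the spread of the gland score, which are not given either. A false-positive rate could be computed only by assuming all of these, so none is quoted.

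**The case against.** The strongest reply is that the paragraph is device-focused shorthand. It tells subjects in general to microwave and apply the compress. Taken literally for every arm, that would have control subjects using the Bruder product, contrary to arm 3. The diary is given to all subjects, arm 3's dose is specified, inclusion criterion 4 and exclusion criterion 10 ask for willingness to comply, and the diary form is not shown. On this view the protocol is merely silent about the cloth.

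Part of this stands. A reader might infer that cloth use goes unrecorded, but the document does not say so, and the form may have a line for it. The shorthand reading still does not close the gap. If the paragraph is about Bruder subjects, so is its compliance check, and nothing else covers control subjects. Willingness at entry is not a record of use.

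Three stronger inferences are also tempting, and the document supports none of them:

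- *That the wording inflates the device's apparent advantage.* Nothing links the sentence to an actual adherence gap, and for the two Bruder groups together the sign may be the reverse.
- *That the missing lens timing in arm 3 biases the gland score.* The protocol gives no effect of timing on that score, and arms 1 and 2 are not matched in timing either.
- *That the primary result is compromised.* The primary endpoint as stated involves no control comparison.

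It is also fair to say that a diary line records use more than it equalises it. A real difference in adherence would remain in an as-randomised comparison. The gain is chiefly that the difference would be visible.

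**Conclusion.** The point holds as a minor one. The protocol states an adherence check for the compress and none for the wash cloth, so monitoring can differ between the Bruder groups and control in the tertiary comparison of total meibomian gland score. This rests on the text alone. The application counts serve only to show that the direction cannot be settled, and they assume 28 treatment days and about equal arms. The lens-timing gap in arm 3 is an inconsistency worth aligning and nothing more.

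**What to change.** Replace the diary compliance sentence with: *Diaries in all three arms record each application of the assigned treatment (compress or wash cloth), and compliance is reviewed in the same way at Visits 2 and 3.*

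As a secondary alignment, give arm 3 the timing of arm 1: ten minutes in the morning before the lenses go in and ten minutes in the evening once they are out. No rule on rewarming the cloth is needed, so heat retention remains part of what is tested.

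The cost is two protocol sentences and one more diary line, with no added visit or procedure. The downside is that monitored control use departs slightly from unsupervised home use and may shrink the apparent advantage of the device.

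### The purpose and primary objective claim an effect in lens wearers with MGD, but none of the 20 eligibility criteria requires MGD or any gland finding

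*Protocol*

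**What the plan says.** Two sentences in the protocol define the target population by MGD. The purpose, at the end of the background, is to assess the product, described as "a warm compress capable of maintain heat effectively, in contact lens wearers with MGD". The primary objective, under Study Objectives, concerns "daily application of the Bruder Moist Heat Compress in subjects with MGD who experience CL discomfort".

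Three other sentences describe the subjects without that qualifier. The design statement under Study Design & Endpoints speaks of "contact lens wearers who report reduced comfortable wearing time by assessing improvement in MG function". The enrolment statement reads "Thirty adults who currently wear contact lenses, who report reduced contact lens wear time will be enrolled in the study". The tertiary objective refers to symptomatic lens wearers and to improving their gland function.

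The background links symptoms to MGD in qualified terms: "Contact lens wearers often report dry eye symptoms and show signs of MGD including gland atrophy", and "in many patients with intolerance to contact lenses, MGD has been observed". The stated mechanism is that "the heat softens meibum in glands that are obstructed allowing for secretion into the tear film".

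Entry is governed by Inclusion Criteria 1 to 8 and Exclusion Criteria 1 to 12. All subjects are examined for eligibility, and the procedure list includes a meibomian gland assessment and meibography.

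**The concern.** A primary objective that names a disease implies that the subjects have it. Here nothing in the eligibility lists ensures this. If the plan were followed exactly, the primary conclusion would be worded for subjects with MGD while resting on subjects admitted without regard to it.

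What is at stake is the scope of the claim. There is also a possible second effect: if part of the benefit comes from clearing obstructed glands, as the background argues, subjects without MGD would pull the average effect down. With about ten subjects per arm, there is little room for that.

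**Working it through.** **Step 1. Count the criteria.** Both lists are numbered without gaps: 8 inclusion + 12 exclusion = 20.

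**Step 2. Ask of each whether it requires MGD or a gland finding.**

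| Criteria | Subject | Requires MGD or a gland finding? |
|---|---|---|
| Inclusion 1, 2, 4 | Age, consent, compliance | No |
| Inclusion 3, 5 | Visual acuity, lens wear habits | No |
| Inclusion 6 | Contact lens dry eye by CLDEQ | No; a questionnaire diagnosis |
| Inclusion 7 | Gap of at least 2 hours between overall and comfortable wear time | No; a symptom threshold |
| Inclusion 8 | Lens fit, material and solution not the cause | No; removes other causes |
| Exclusion 1, 3 | Interfering systemic disease; active ocular conditions | No; removes other causes |
| Exclusion 4 | Clinically significant ophthalmic abnormality | No; no exception for MGD stated |
| Exclusion 2, 5 to 12 | Pregnancy, lens or solution changes, lens type, medication, other trials, surgery, compliance, plugs, omega-3 | No |

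Result: 0 of 8 inclusion and 0 of 12 exclusion criteria, so 0 of 20.

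**Step 3. Do the symptoms imply MGD?** In the protocol's own terms, no. The background says *often* of lens wearers in general and *many* of intolerant wearers. Neither means all. A wearer with normal glands, a qualifying CLDEQ result and a 2-hour gap can meet every criterion.

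**Step 4. Does the eligibility examination close the gap?** An examination selects subjects only through a criterion. The one criterion tied expressly to abnormalities found on examination is Exclusion 4, and it works in the opposite direction: unless MGD is exempted, a subject whose MGD is judged clinically significant could be turned away. This applies to the protocol as it stands.

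**Step 5. Can the dilution be sized?** Let p be the share of enrolled subjects with MGD, D1 the treatment effect in them and D0 the effect in the others. The trial estimates on average

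p × D1 + (1 − p) × D0.

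This equals D1 only if p = 1 or D0 = D1. The protocol gives none of p, D1 or D0, nor a standard deviation, so neither the shortfall nor any loss of power can be calculated. The protocol states no figure on this point that could be reproduced.

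**The case against.** The strongest reply is that the criteria select MGD indirectly. Inclusion 8 and Exclusions 1 and 3 remove lens-related, systemic and other ocular causes of discomfort, the glands are examined, and an unwritten MGD screen is plausible. Part of this stands: those three criteria may raise the share with MGD, and the gap may be a drafting omission, not a decision to enrol a mixed group. But removing some alternative causes does not establish MGD, and an unwritten screen is not part of the plan.

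A second reply is that a statistical analysis plan, not available here, could adjust for baseline gland score or define a subgroup by it. A subgroup could support an MGD claim, at a cost in numbers when arms hold about ten subjects. It would still not change who is enrolled or what the primary objective says.

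A reader might go further and infer that the protocol sets out two competing populations. The text does not support that. The design statement, enrolment statement and tertiary objective are less specific, but none seeks subjects without MGD, and two of them speak of improving gland function, which fits poorly functioning glands. The defect is a missing link between the claim and the entry criteria.

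**Conclusion.** The point holds and should be fixed. The purpose and primary objective name MGD; 0 of 20 criteria require it; and Exclusion 4, read literally, could remove some subjects who have it. A result from this trial would apply to the symptomatic wearers enrolled and would not support a claim limited to subjects with MGD.

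Two stronger conclusions are tempting and unsupported. The trial is not invalid: randomisation still gives a fair comparison among those enrolled. Nor can it be said that power is lost. That needs subjects without MGD to be enrolled and to benefit less, and the document gives no figure for either.

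The conclusion rests on the eligibility lists being complete as shown, which their unbroken numbering supports.

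**What to change.** Reconcile the purpose, the primary objective and the eligibility lists, including whether MGD falls under Exclusion 4.

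**The cheap way: reword the claim.** Remove the MGD qualifier from the purpose and primary objective. In the purpose, the design statement's own description of wearers with reduced comfortable wearing time can replace it. Report baseline total gland score by arm so that readers can see how much gland disease was present; the tertiary endpoint already needs that score at baseline. Cost: two sentences and one table row. The claim then says less about MGD, and any dilution remains, because rewording corrects the scope of the claim and not the make-up of the sample.

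**If the MGD claim is to be kept: add an entry criterion.** Base it on the gland assessment already listed, with the scale and cut-off defined by the investigator. No new procedure is needed. However, screening and randomisation share one visit ("Visit 1 (Screening & Randomization, Day 1"), so the assessment would have to be scored before allocation at that visit, and more subjects would fail screening. That is a trade-off for the sponsor to weigh.

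### The primary endpoint names no contrast, and no stated endpoint compares comfortable wear time between the Bruder compress and the wash cloth control

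*Protocol*

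**What the plan says.** Study Design & Endpoints describes a three-arm randomised controlled study of thirty adults, about ten per arm. The third arm is "Application of warm wash cloth twice daily (ten minute application each time) for one month (control group".

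The objectives and endpoints are:

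- **Primary.** The objective is to show that daily use of the compress "can result in an increase in comfortable contact lens wear time". The endpoint is "Mean change from baseline in the duration of subject-reported comfortable contact lens daily wear time (hours per day) at the week four visit".
- **Secondary.** The objective compares once-daily with twice-daily use of the compress. The endpoint is "Mean change in comfortable contact lens wear time (hours per day) in twice daily application group compared to once daily application group".
- **Tertiary.** The objective is "To show that the Bruder Moist Heat Compress is an effective treatment for improving meibomian gland function in symptomatic contact lens wearers". The endpoint is "Mean change in total meibomian gland score in treatment groups using the Bruder Moist Heat Compress compared to controls from baseline to four weeks".

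The design statement says that benefit will be evaluated "by assessing improvement in MG function and comfortable contact lens wearing time after one month of daily warm compress application". It names no comparator for that improvement.

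**The concern.** The protocol writes a contrast into its secondary and tertiary endpoints but not into its primary one. As a result, no stated endpoint sets the main outcome, comfortable wear time, in the compress arms against the same outcome in the control arm.

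At stake is what a positive primary result would mean. A rise from baseline in the compress arms could come from at least three sources that are not specific to the Bruder device:

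- **Heat in general.** The introductory text says of the whole class: "With good patient compliance, warm compresses have been shown to be an adequate supplemental therapy for MGD". The control is itself a warm compress.
- **Regression to the mean.** Inclusion criterion 7 admits only subjects whose overall wear time exceeds their comfortable wear time by at least 2 hours. Part of a gap selected for being large can be expected to shrink on remeasurement.
- **Reporting effects.** The outcome is self-reported.

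Comparing randomised arms removes regression to the mean and any response the arms share. A before/after change removes neither.

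**Working it through.** **1. Which groups does each endpoint compare?**

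| Endpoint | Variable | Groups compared |
|---|---|---|
| Primary | Comfortable wear time | None named |
| Secondary | Comfortable wear time | Twice daily v once daily |
| Tertiary | Total meibomian gland score | Compress arms v controls |

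The wash cloth is also applied twice daily, so the secondary endpoint taken alone might be misread as involving it. The secondary objective settles this: both schedules are compress schedules. The cell for comfortable wear time, compress v wash cloth, is therefore empty.

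**2. Does other text fill the gap?** The primary objective speaks of an increase and names no comparator. The design statement speaks of improvement after a month of use and names none either. The label of a randomised controlled study points to a comparison but does not say which one, or whether the two compress arms are combined for it.

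**3. Is there a figure to reproduce?** No. The protocol states no significance level, power, effect size, standard deviation or dropout rate. The size of a non-specific rise cannot be derived from it either: that needs the spread of the wear-time gap, its retest correlation, and the share of the gap that comes from comfortable time.

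**4. What could the missing contrast resolve?** This needs only the arm sizes plus assumptions: two-sided 5% level, 80% power, no dropout, and adjustment for one baseline covariate. Effects are in units of the residual SD.

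- Standard error = √(1/n₁ + 1/n₂). For 20 v 10: √(0.05 + 0.10) = 0.387. For 10 v 10: √(0.10 + 0.10) = 0.447.
- Residual degrees of freedom = N − 3 (two group means and one slope): 30 − 3 = 27 and 20 − 3 = 17.
- 95% confidence interval half-width = t(0.975) × SE: 2.052 × 0.387 = 0.79 and 2.110 × 0.447 = 0.94.
- Difference giving 80% power, from the noncentral t distribution: 1.13 (20 v 10) and 1.33 (10 v 10).

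For comparison, without baseline adjustment and in units of the SD of the change score, the between-arm figures are 1.12 (20 v 10) and 1.32 (10 v 10). A before/after test within the compress arms reaches 80% power at 0.66 (n = 20) or 1.00 (n = 10). The before/after reading is thus easier to satisfy, even before any non-specific rise is counted.

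**The case against.** The best defence is that the contrast is implied and its detail belongs in a SAP that is not shown. The primary endpoint fixes variable, unit, time point and summary, which is the usual form of an endpoint definition. The trial is called randomised and controlled, and the wash cloth is labelled the control. The rationale is also comparative: results are said to vary with heating method and with how well heat is held. The tertiary pair shows the drafting habit, since its objective names no comparator and yet its endpoint is against controls. The secondary endpoint had to name its groups because it departs from treatment versus control.

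Much of this stands. It makes between-arm intent plausible, and it means the wording of the primary objective is weak evidence on its own. Choice of model and covariates can be left to a SAP. What does not stand is that the gap is mere SAP detail. The protocol treats the comparison as part of an endpoint in two cases out of three and omits it for the one that matters most. The two available readings can lead to opposite conclusions.

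A reader might go further and infer that the sponsor plans a before/after test and will leave the control unused for the main outcome. The protocol states no test and no success rule, so that would be an inference from silence. Nor does the text imply that the wash cloth and compress arms would rise equally, given what it says about heating methods.

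**Conclusion.** The point holds as a defect of wording in the primary endpoint and objective. The contrast between compress and wash cloth on comfortable wear time is not stated anywhere, and the literal text permits a before/after conclusion that would not show an advantage over the control. It should be fixed. Confidence is moderate, because a between-arm intention is plausible and an unseen SAP may already supply the contrast.

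It is tempting to attach a false-positive rate to the before/after reading. The documents do not support one: every input would have to be assumed, and no success rule is stated against which an error could be counted. The conclusion rests on the text alone. The only figures offered are the precision figures, which depend on the stated arm sizes and on the assumed 5% two-sided level, 80% power, full follow-up and one baseline covariate.

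**What to change.** - **Primary endpoint.** Define it as the difference, Bruder compress minus warm wash cloth, in mean change from baseline to week four in self-reported comfortable wear time (hours per day), preferably adjusted for baseline comfortable wear time.
- **Primary objective.** Add: compared with a warm wash cloth. The rest can stay.
- **Arms compared.** State in advance whether the compress arms are pooled (20 v 10), which suits an objective about daily use but mixes frequencies, or which single arm is compared (10 v 10). The twice-daily arm matches the control's frequency.
- **Within-arm changes.** Keep them descriptive.
- **SAP.** If it already makes this comparison, align the protocol to it.

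The change costs the rewording of one endpoint and one objective, with no new visits or data. It has three downsides. Precision is low, as shown above, so only a large difference could be detected reliably and the interval will be wide. The question narrows to gain over another warm compress. And because the arms are visibly different and the outcome is self-reported, a differential placebo response is not fully removed.
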